- 7. An estimate of the hazard of development to COVID-19 compatible symptoms, or COVID-19 related hospitalisation, among individuals with a positive vs negative laboratory and HTK anti-coronavirus antibody results, alone and in combination with SARS-CoV-2 responsive T cell numbers;
- 8. A panel of plasma which can be used to evaluate the accuracy of any next-generation immunochromatographic kits in a 'bridging' validation / verification study, for quality assurance, and lot qualification.

Study Design

Methods: Test evaluation, including a prospective cohort study of high risk (healthcare workers) and lower risk (e.g. police) populations for COVID-19.

Population: The test evaluation population will reflect the population projected to use the home testing service in the initial stages of HM Government test rollout, which is likely to be front line workers such as healthcare staff and police/fire/rescue officers. A representative sample from a group of organisations will be recruited if possible.

Subsequently, testing may be extended to the general public, once the first two target groups have been studied.

In addition, a selection of individuals with previous positive SARS-CoV-2 tests ("known positives") from OLS-WS-2 (Antigen testing) (at least 2 weeks after initial infection) may be included into the population.

Evaluating Detection of SARS-CoV-2 antibodies using home test kits (EDSAB-HOME study)

Protocol 30.05.2020 Version 04.03

Inclusion criteria:

- Currently working at their place of work;
- Aged 18 years or older;
- Able to read and English, so as to understand the protocol;
- Has an in-use personal email address and mobile phone.

Exclusion criteria:

- Is currently experiencing COVID-19 compatible symptoms.
- Has experienced COVID-19 compatible symptoms in the last seven days;
- Meets definition of "exceptionally vulnerable" on medical grounds, including immunosuppression, previous oncological treatments these people should not be at work anyway;
- Unable to read normal sized print with glasses;
- Taking part in vaccine studies.

Methodology

Recruitment:

PHE will aim to recruit initial users of the HTK program, with the overall aim of obtaining a representative sample of initial intended users. This will comprise of three key cohorts, with different expected prevalence, allowing some exploration of whether sensitivity may vary by severity:

- Healthcare workers (1,500 persons). All individuals working on site will be eligible to enrol.

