- Police workers (1,000 persons) [or other cohort of non-healthcare workers]. All individuals working on site will be eligible to enrol.
- General population, the recruitment of which will be considered at a later date once the first two groups have been studied.

Additionally, a fourth cohort will be approached. These are individuals who have previous tested positive as part of health care worker screening, and whose details are known to the NHS Business Services Authority (NHSBSA). The DHSC has undertaken legal review, and has confirmed to us that their processing of the personal details of these individuals for this purpose is lawful, and that they are prepared to send a communication to them on our behalf. We will attempt to recruit up to 500 such workers.

Recruitment strategy: Workplace based recruitment

Senior leadership (CEO or equivalent) from selected workplaces will be sent a letter signed by senior leadership in DHSC inviting their institution to take part in the study and their specific ask for taking part. They will have the opportunity to have a phone call with senior leadership in DHSC to discuss the proposed processes and answer any questions they may have.

If they agree to take part, they will be sent a template email to send out to their employees. This will include information on the criteria for taking part, the participant information sheet, and links to the consent form, online questionnaire, and appointment booking system. They will also be sent a template poster which can be put up in their place of work. This will emphasise to their staff that the study is voluntary, and they have no obligation to take part. Depending on recruitment rates, we may restrict recruitment to a convenience sample of the first 100-150 people to book an appointment per institution. Additional, walk in slots may be available, depending on logistical capacity.

Evaluating Detection of SARS-CoV-2 antibodies using home test kits (EDSAB-HOME study)

Protocol 30.05.2020 Version 04.03

Recruitment strategy: Workplace based recruitment

DHSC, in collaboration with the NHSBSA, will send a closely related template email to that sent out by NHS Trusts to individuals who have previously tested positive.

Three stages:

The study will take place in three stages (Figure 1):

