 The anticipated initial users of the service (including up to 500 "known positives") are recruited (2,500 persons) prior to the HTKs becoming available, and invited to attend a community testing centre on specific day(s). At the centres, metadata will be collected on all individuals (in the form of an electronic questionnaire) and a venous blood sample taken.

In a small number (n ~ 100) of individuals, a capillary blood sample and dried blood spot (DBS) will be taken. This will allow assay optimisation for enzyme immunoassays which may in future use capillary blood samples.

The blood samples will be tested with one or more commercial EIAs. These include products by EuroImmun (anti-Spike) Roche (anti-N) Abbott (anti-N).

Emerging data indicates that anti-N assays have very good performance, with enhanced sensitivity relative to anti-S assays. For all the assays, sensitivity, particularly early in disease and in cases of asymptomatic infection, is less well characterised.

We will use a single assay with the highest published performance available, which we will refer to as the High Performance Assay (HPA). We envisage this will be one of the two available anti-N EIAs. Subject to availability, we will perform both an anti-S and anti-N assay on all samples as well, but the initial analysis of the HTK will be against the HPA. Other experimental assays under development by the DHSC project or PHE may also be used. A plasma bank will be set up, ready to be tested with the HTK in the laboratory once available. The clinical performance of the HTK will be estimated in two separate analyses (1) assuming the HPA is 100% sensitive and specific (which may, however, be incorrect); and (2) Bayesian evidence synthesis methods incorporating other data sources (see below). (Objective 1, 6, 7).

The capillary blood samples will be used to compare EIA signals between samples derived from DBS, venous plasma and capillary plasma samples as part of a proof-of-concept, methods development approach. The 100 sample size is based on the need for at least 10 positives, and is based on an assumed 10% seroprevalence. We will modify the number of capillary samples taken to ensure sufficient positive samples are available based on seroprevalence data.

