Data will be entered in Snap Survey or another suitable technical platform and stored on a secure PHE server using a relational database management system. Only those who are conducting data management, cleaning or analysis will have access to the data. Any data shared outside of PHE will have a suitable data sharing agreement in place, and only pseudo-anonymised datasets will be shared.

We aim to maintain the volunteer bank, which contains identifiable information, for up to 2 years, whereby volunteers may be recalled to test new antibody devices as they become available. One year following the conclusion of the volunteer bank all personal identifiable information will be removed.

Data management will be performed in R and statistical analysis using a combination of R and Bayesian statistical software, WinBUGS. Laboratory methods will follow the requirements of ISO15189.

Data management will follow PHE Information Governance and GDPR requirements.

Statistical Analysis

An initial descriptive analysis will describe the cohort by age, gender, ethnic group, occupation, recent symptoms and previous exposure to SARS-CoV-2 assessed using symptoms, and enzyme immunoassay and T-SPOT coronavirus assays.

The EDSAB-HOME project is intended as part of a programme delivering high quality information to support rapid licensure of HTKs. These may come from different sources, with different amounts of in vitro data comparing HTK vs. other standards, prior to EDSAB-HOME study investigators become involved. Essentially, some of the objectives described in Objective 1 may already have been met to a standard acceptable to regulators for some products to which the EDSAB-HOME protocol is applied. The decision as to whether the activities described in Objective 1 will be conducted, and on what scale, will made by the DHSC who are in charge of the project, in conjunction with the MHRA. The EDSAB-HOME investigators will provide professional advice and assist DHSC in delivering the overall project goals.

Objective 1

To describe the accuracy of the HTKs in detecting anti-SARS-CoV-2 antibody, and in detecting previous SARS-CoV-2 infection, when read by a trained professional;

For each sub-population – and also aggregated across all individuals - results (positive / negative) on the HTK will be tabulated against results on the HPA (dichotomised at a pre-specified level), of format in Table 1, where N is the number of samples analysed:

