Evaluating Detection of SARS-CoV-2 antibodies using home test kits (EDSAB-HOME study)

Protocol 30.05.2020 Version 04.03

Table 1

	Laboratory-based assay	Laboratory-based assay	Total
	positive	negative	
Home test kit positive	a	b	a + b
Home test kit negative	c	d	c + d
Total	n+ = a + c	n- = b + d	N = a + b + c + d

We will produce estimates, with 95% credible intervals (Cr-Is), of the test sensitivity and specificity of the HTK, and of the implied Positive Predictive Value (PPV) and Negative Predictive Value (NPV), across a range of values of prevalence or pre-test probability.

We will produce similar analyses for T-SPOT coronavirus results.

We will assess evidence for whether test accuracy varies by sub-population and by key variables from the questionnaire such as reporting of previous COVID-19 like symptoms.

Analysis 1a

In Analysis 1 we will assume that the laboratory based assay, HPA, dichotomised at a pre-specified threshold, is a "gold standard" reference test, i.e. has 100% sensitivity and 100% specificity in detecting anti-SARS-CoV2 antibody.

Sensitivity and specificity of the HTK can then simply be estimated by the proportion of HPA positive samples that are positive on the HTK (i.e. Table 1: a/n+); and the proportion of HPA negative samples that are negative on the HTK (i.e. Table 1: d/n-), respectively. 95% Cr-Is around estimates will be estimated through fitting binomial likelihoods in WinBUGS. The PPV and NPV will be calculated by application of Bayes' rule within the WinBUGS model, such as to produce Cr-Is that account for sampling uncertainty in both sensitivity and specificity.

Estimates of each of these quantities will be provided both 'overall' and also stratified by sub-population or and/or other key variables from the questionnaire.

We will produce similar analyses using T-SPOT coronavirus results.

Sample Size for Analysis 1 of Objective 1

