Sample size calculations for this study are challenging because of the lack of a gold standard test, and the fact that prevalence in the study population is both unknown and increasing over time. The following calculations assume that the HPA laboratory-based test is 100% sensitive and 100% specific, which is known not to be the case. The calculations are therefore no more than illustrative. We assumed that the true sensitivity and specificity of the HTK are both 98%. These are the minimum values currently considered acceptable by the MHRA (18/04/2020). The performance metric of the most interest is the PPV, defined as the probability that a person who tests positive does in fact have antibodies. Table 2 shows the expected 95% confidence intervals for sensitivity, specificity and PPV which would be obtained for a sample size of 1000 or 2500 participants, under various assumed values of prevalence in the study population. If we were to consider 90% PPV acceptable, and prevalence in the study sample was 20%, we would require 2,500 participants to obtain a 95% CI which was wholly above 90% PPV.

Evaluating Detection of SARS-CoV-2 antibodies using home test kits (EDSAB-HOME study)

Protocol 30.05.2020 Version 04.03

Table 2 The expected 95% confidence intervals (CIs) around estimated sensitivity, specificity and PPV under potential sample sizes of n = 1000 and n = 2500, assuming true sensitivity and specificity are both 98%.

	Study size	of n = 1000		Study size of	of n = 2500	
Prevalence in study population	Sensitivity 95% Cl	Specificity 95% CI	PPV in study population: estimate (95% CI)	Sensitivity 95% CI	Specificity 95% CI	PPV in study population: estimate (95% CI)
5%	0.93,1.00	0.97,0.99	0.72 (0.61,0.82)	0.95,1.00	0.97,0.99	0.72 (0.65,0.79)
10%	0.95,1.00	0.97,0.99	0.85 (0.78,0.91)	0.96,1.00	0.97,0.99	0.85 (0.80,0.89)
15%	0.95,1.00	0.97,0.99	0.90 (0.85,0.94)	0.96,0.99	0.97,0.99	0.90 (0.87,0.92)
20%	0.96,1.00	0.97,0.99	0.93 (0.89,0.96)	0.97,0.99	0.97,0.99	0.92 (0.90,0.95)
25%	0.96,1.00	0.97,0.99	0.94 (0.91,0.97)	0.97,0.99	0.97,0.99	0.94 (0.92,0.96)

Test performance may vary across populations, e.g. due to variation in underlying severity of disease. To allow exploration of this, initially we propose a cohort of 1500 healthcare workers and 1000 police officers, with later possible extension to the general public.

Analysis 1b

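### The overall accuracy estimates in Analysis 1a pool participants selected for a previous positive test with the workplace cohorts, so overall sensitivity depends on how many of them enrol

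*Protocol*

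**What the plan says.** Under Statistical Analysis, Objective 1, HTK results are cross-tabulated with HPA results for each sub-population "and also aggregated across all individuals". Analysis 1a takes the HPA as a perfect reference for antibody. Sensitivity is a/n+ over all HPA positives and specificity is d/n− over all HPA negatives. "Estimates of each of these quantities will be provided both 'overall' and also stratified by sub-population" or by questionnaire variables.

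The participants come by two routes. The workplace cohorts are open to everyone on site. For the other route, the Recruitment section says "Additionally, a fourth cohort will be approached", made up of health care workers with a previous positive test, and "We will attempt to recruit up to 500 such workers". The Population paragraph describes such people as coming "from OLS-WS-2 (Antigen testing) (at least 2 weeks after initial infection) may be included into the population". Their known-positive status is used explicitly only in Analysis 2. No sentence excludes, weights or separates them in the overall Analysis 1a figures.

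The totals do not agree. Stage one says that intended users, with the known positives counted among them, "are recruited (2,500 persons) prior to the HTKs becoming available". The sample size section says "initially we propose a cohort of 1500 healthcare workers and 1000 police officers", which already makes 2,500 without them.

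**The concern.** The Recruitment section aims for a representative sample of initial intended users. People selected on a previous positive result are not a sample of that population, and they supply HPA positives at a far higher rate than the workplace cohorts. A pooled sensitivity is then a weighted average of two groups, with weights set by recruitment success and not by the intended-use population. The sample size section says that performance may vary with the severity of disease, so equal sensitivity in the two groups cannot be taken for granted.

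The laboratory comparison is meant to show whether the kit meets the target product profile before stage two. The sample size section gives 98% as the minimum acceptable sensitivity and specificity. The protocol does not say which estimate decides, so a pooled figure could be read against that threshold.

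Secondarily, a known positive whom the HPA misses falls into n−. If the HTK detects that person, the result is scored as a false positive.

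**Working it through.** **The plan's own figure.** Table 2, n = 2,500, prevalence 20%, sensitivity and specificity 98%. With p ± 1.96√(p(1−p)/n):
- Sensitivity, n+ = 500: 0.968–0.992 (Table 2: 0.97–0.99).
- Specificity, n− = 2,000: 0.974–0.986 (Table 2: 0.97–0.99).
- PPV = 490/(490 + 40) = 0.925, interval 0.902–0.947 (Table 2: 0.92, 0.90–0.95).

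The figures reproduce, so the same interval formula is used below.

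**Inputs.**
- K = 500 known positives, a ceiling (Recruitment).
- M = 2,000 others if the 500 lie inside the 2,500 (stage one), or 2,500 if they are additional (Recruitment, sample size section).
- Seroprevalence π in the others: 10%, the value assumed in stage one for the capillary subsample; Table 2 spans 5–25%.
- s = proportion HPA-positive among known positives. This is an assumption, 0.73–0.98. Appendix One gives 73% for one assay at 15–28 days and about 80% for past disease.

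**Share of HPA positives who are known positives** = Ks/(Ks + Mπ), with all 500 enrolled and s from 0.73 to 0.98:

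| π | M = 2,000 | M = 2,500 |
|---|---|---|
| 5% | 78.5–83.1% | 74.5–79.7% |
| 10% | 64.6–71.0% | 59.3–66.2% |
| 15% | 54.9–62.0% | 49.3–56.6% |
| 20% | 47.7–55.1% | 42.2–49.5% |
| 25% | 42.2–49.5% | 36.9–43.9% |

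With 250 enrolled and π = 10%, the share is 42–55% over both values of M.

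**Effect on overall sensitivity.** Assume HTK sensitivity of 98% in known positives and 90% in other HPA positives, with s = 0.9, M = 2,000 and π = 10%, so that the others contribute 200 HPA positives:
- None enrolled: 180/200 = 90.0%, interval 0.858–0.942.
- 250 enrolled: (180 + 225 × 0.98)/425 = 94.2%.
- 500 enrolled: (180 + 450 × 0.98)/650 = 95.5%, interval 0.940–0.971.

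The kit and the intended users are the same in all three lines. Only enrolment changes.

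**Effect on apparent specificity.** Known positives in n− number K(1 − s). Let d be the assumed probability that the HTK is positive in them, with 98% specificity elsewhere, M = 2,000 and π = 10%. Specificity = 1 − (36 + K(1 − s)d)/(1,800 + K(1 − s)):

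| s | known positives in n− | d = 10% | d = 50% |
|---|---|---|---|
| 0.98 | 10 | 0.980 | 0.977 |
| 0.90 | 50 | 0.978 | 0.967 |
| 0.80 | 100 | 0.976 | 0.955 |

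The shift runs from about zero to 2.5 points. The 73% figure is left out here because it belongs to an anti-S assay in early sera, whereas the protocol expects the HPA to be an anti-N assay.

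**The case against.** **Much of the separation is already planned.** Estimates by sub-population are listed, the known positives are called a cohort, Analysis 1b reports accuracy against confirmed cases, and Analysis 2 uses known-positive status. No passage calls the aggregate the headline result. This stands as a description, but none of it corrects the pooled figure. Nor are the known positives named as a stratum. If they were counted among the 1,500 healthcare workers, then with s = 0.9 and 10% seroprevalence in the other 1,000 they would make up 450 of 550 HPA positives (82%) in that stratum too.

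**The sensitivity gap is assumed.** This stands. Appendix One reports that mild cases later reach titres similar to severe ones. The known positives must be at work and at least two weeks past infection, so they are not shown to be a severe group. A reader might infer that pooling certainly inflates sensitivity. The documents support only that it does so if sensitivity is lower without a prior diagnosis.

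**Specificity and PPV.** A reader might infer that both will be clearly too low. The documents do not support this. Analysis 1a targets antibody with the HPA taken as perfect, so a past case without antibody belongs in n−. Error from an imperfect HPA is left to Analysis 2 and would also affect infected workplace participants. The protocol expects positive dependence between the HTK and other antibody tests, which points to small d. PPV is computed across a range of prevalences, and the sensitivity illustration barely moves it: at 10% prevalence and 98% specificity, from 0.833 (sensitivity 90%) to 0.841 (95.5%).

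**Conclusion.** The point holds for overall sensitivity. As written, the overall Analysis 1a estimates mix people selected on a previous positive test with cohorts recruited irrespective of infection status. At 10% seroprevalence and full recruitment, the selected group supplies 59–71% of HPA positives. The resulting sensitivity does not describe the intended users unless the two groups happen to share the same sensitivity. The size of any error depends on that unknown difference; 95.5% against 90% is an illustration, not a forecast.

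It would go too far to say that known positives dominate in every case. The 500 is a ceiling, and the share is 37–55% at 20–25% seroprevalence. It would also go too far to call the group PCR-confirmed, since the Population paragraph refers to antigen testing. The specificity effect is secondary and should be quoted only as a range.

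The conflict over whether the 500 lie within the 2,500 is textual and needs no assumption. It leaves the weight of this group unfixed.

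**What to change.** - State that the overall Analysis 1a estimates use only the workplace cohorts recruited irrespective of infection status.
- Name the known-positive cohort approached through the NHS Business Services Authority as its own stratum, and report HTK and HPA results in it separately.
- Combine the two groups only in Analysis 2, where known-positive status is modelled.
- Reconcile stage one with the Recruitment and sample size sections on whether the 500 are within the 2,500 or additional to it.

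The cost is precision in overall sensitivity. At 98% sensitivity, 10% seroprevalence and 2,000 workplace participants, n+ falls from 650 (with s = 0.9) to 200, and the interval widens from about 0.969–0.991 to 0.961–0.999. With 2,500 workplace participants, n+ = 250 and the interval is about 0.963–0.997. No extra data collection is needed.

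### At 20% prevalence, 2,500 participants give only about an even chance of the PPV interval wholly above 90% that the sample size text says they would obtain

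*Protocol*

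**What the plan says.** The relevant text is the section on sample size for Analysis 1 of Objective 1, with Table 2.

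- **Kit accuracy:** "We assumed that the true sensitivity and specificity of the HTK are both 98" per cent.
- **Reference standard:** "The following calculations assume that the HPA laboratory-based test is 100% sensitive and 100% specific". The text admits this is untrue and therefore calls the calculations illustrative.
- **Type of figure:** "Table 2 shows the expected 95% confidence intervals for sensitivity, specificity and PPV which would be obtained" at 1,000 or 2,500 participants, for five prevalences from 5% to 25%.
- **Threshold:** introduced conditionally, "If we were to consider 90% PPV acceptable", for the case in which "prevalence in the study sample was 20" per cent.
- **Conclusion:** "we would require 2,500 participants to obtain a 95% CI which was wholly above 90% PPV".

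At 20% prevalence the Table 2 PPV entry for 2,500 participants begins "0.92 (0.90,0.95", and the entry for 1,000 begins "0.93 (0.89,0.96". The section names PPV as the performance measure of greatest interest. It does not say how the table's intervals were computed and gives no probability of meeting the criterion. Analysis 1a plans credible intervals for PPV from binomial likelihoods and Bayes' rule.

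**The concern.** The conclusion describes an interval that 2,500 participants would obtain, but the table shows its lower limit as 0.90, which is the threshold itself. At two decimals a reader cannot tell whether the interval is wholly above 90%. When an expected limit falls on a threshold, the observed limit lands on the wrong side in roughly half of all studies, even if every assumption is true.

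This sentence is the one place where 2,500 is tied to a success criterion. A reader who takes it as assurance could treat an interval that dips below 90% as evidence against the kit. Under the protocol's own assumptions, that result is about as likely as not.

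**Working it through.** **Inputs** (all from the sample size section): N = 2,500; prevalence 20%; sensitivity and specificity 0.98; perfect reference test; threshold 0.90; two-sided 95% interval.

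**1. Expected counts**
- Reference positive: 0.20 × 2,500 = 500. True positives: 0.98 × 500 = 490.
- Reference negative: 2,000. False positives: 0.02 × 2,000 = 40.
- PPV = 490 / 530 = 0.9245.

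**2. Reproducing the printed interval (Wald)**
- SE = √(0.9245 × 0.0755 / 530) = 0.01147.
- 0.9245 ± 1.96 × 0.01147 = 0.902 to 0.947, which rounds to the printed 0.90 and 0.95.
- Over the whole table, Wald limits match 18 of the 20 PPV limits to two decimals. Average simulated exact limits match 13 and average Wilson limits match 7.

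**3. The same cell by other methods**

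| Method | 95% limits |
|---|---|
| Bayes' rule, fixed prevalence, delta method, linear scale | 0.9031–0.9460 |
| Wald | 0.9020–0.9470 |
| Bayes' rule, beta posteriors, Jeffreys priors | 0.9011–0.9440 |
| Bayes' rule, beta posteriors, uniform priors | 0.9001–0.9431 |
| Bayes' rule, fixed prevalence, delta method, logit scale | 0.9001–0.9434 |
| Jeffreys on 490/530 | 0.8997–0.9447 |
| Wilson | 0.8989–0.9441 |
| Clopper-Pearson | 0.8986–0.9455 |

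The lower limit runs from 0.899 to 0.903. The method alone decides on which side of 0.90 it falls.

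**4. Chance that the observed lower limit exceeds 0.90**

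Approximation for Wald: the expected lower limit exceeds the threshold by 0.9020 − 0.9000 = 0.0020. Divided by the SE, 0.0020 / 0.01147 ≈ 0.18, and Φ(0.18) ≈ 0.57.

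This was checked by simulation, drawing the number of reference positives from Bin(2,500, 0.2), true positives from Bin(positives, 0.98) and false positives from Bin(negatives, 0.02):

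| Method | Chance at N = 2,500, prevalence 20% |
|---|---|
| Clopper-Pearson, Wilson | 47% |
| Jeffreys on TP/(TP+FP) | 50% |
| Bayes' rule, logit scale | 51% |
| Wald | 57% |
| Bayes' rule, linear scale | 61% |

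**5. Sensitivity to prevalence and N**
- N = 2,500, prevalence 25%: about 98–99%.
- N = 2,500, prevalence 15%: about 1–2%.
- N = 2,500, prevalence 10%: 0%. Table 2 itself gives limits of 0.80 and 0.89 there.
- An 80% chance at 20% prevalence needs about 4,000 (Bayes' rule, linear scale), 4,500 (Wald) or 5,200 (Wilson, exact).

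**The case against.** The strongest defence is that the protocol does what it says. It labels the intervals as expected, claims no power and calls the exercise illustrative. Sizing an accuracy study on expected precision is legitimate. The 90% PPV threshold is hypothetical: entry to stage two depends on the Target Product Profile, and no decision rule in the document uses PPV above 90%. Table 2 also shows sensitivity and specificity precision and several prevalences, so a reader can see that the 10% and 15% rows fall short. All of this stands, and it limits the severity.

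Three stronger readings are tempting, and the document does not support them.

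- **That the printed interval is wrong because the true lower limit is 0.899.** That value arises only with Wilson, Agresti-Coull or exact limits, which fit Table 2 less well. Wald gives 0.902, and the beta-posterior form of the planned Bayes' rule analysis gives about 0.900–0.901 with uniform or Jeffreys priors. The expected interval just excludes 90% by those methods.
- **That the study is too small and needs 5,000 or more.** This would follow only if 90% PPV were an adopted criterion with a required probability of success. It is neither.
- **That the plan claims assurance outright.** The wording permits that reading, but it promises no probability.

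The defence does not cover one thing. The illustrative label is drawn from the imperfect reference test, and the section separately admits that prevalence is unknown. Neither caveat tells the reader that, with a perfect reference and exactly 20% prevalence, the result is still close to a coin toss.

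**Conclusion.** The printed figure stands, but the conclusion drawn from it needs qualifying. At 20% prevalence with 98% sensitivity and specificity, 2,500 participants give an expected PPV interval whose lower limit is within about 0.003 of 90%. The probability of an observed interval wholly above 90% is about one half (47–61% by method). This holds for every interval method tried.

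It rests on the protocol's own assumptions: perfect reference test, exact 98% accuracy, and independent binomial sampling. It changes steeply with prevalence, from 1–2% at 15% to 98–99% at 25%. The prevalence reached will depend on background seroprevalence (the capillary sub-study assumes 10%) and on how many of the up to 500 known positives enrol.

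Severity is minor to moderate. The weakness is a size statement that can be read as assurance, together with a table too coarse to show how narrow the margin is.

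**What to change.** Keep N = 2,500 and change the text and table only.

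1. Restate the sentence as expected precision, for example: *With 2,500 participants and 20% prevalence, the expected 95% interval for PPV only just excludes 90%, and the probability that the observed interval lies wholly above 90% is about 50%.*
2. Name the interval method, preferably the Bayes' rule interval planned in Analysis 1a, so that the table and the analysis agree. Quote the probability for that method.
3. Show the PPV limits in Table 2 to three decimals by that method.
4. Add a column to Table 2 with the probability of meeting the 90% criterion at each prevalence and sample size.

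Do not present 0.899–0.946 as the single correct interval. It is the exact (Clopper-Pearson) result and matches neither Table 2's apparent method nor the planned analysis.

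The cost is a reworded sentence, a recalculated set of PPV limits, one added column and a less favourable stated figure. No participants are added and the design does not change.

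### Table 2's expected confidence limits look like sampling ranges of the estimate, so the lower limits for sensitivity are optimistic when few participants are antibody-positive

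*Protocol*

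**What the plan says.** The Protocol, under Sample Size for Analysis 1 of Objective 1, states: "Table 2 shows the expected 95% confidence intervals for sensitivity, specificity and PPV", for 1000 or 2500 participants and "under various assumed values of prevalence in the study population". The table title repeats this: "The expected 95% confidence intervals (CIs) around estimated sensitivity, specificity and PPV", for "potential sample sizes of n = 1000 and n = 2500", "assuming true sensitivity and specificity are both 98" per cent. No interval method is named.

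The calculations "assume that the HPA laboratory-based test is 100% sensitive and 100% specific". The section calls them illustrative for that reason.

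From the table it concludes that, at 20% prevalence, 2,500 participants are needed for a PPV interval lying entirely above 90%.

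The interval planned for the analysis is given under Analysis 1a: "95% Cr-Is around estimates will be estimated through fitting binomial likelihoods in WinBUGS". The prior is not stated.

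**The concern.** An expected confidence interval tells the reader how wide the reported interval should be. A percentile range of simulated estimates tells the reader where the point estimate is likely to fall. With a true value of 98% and few positives the two differ. The estimate's distribution piles up against 1, while a sound interval around 49 out of 50 reaches further down.

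Two features of Table 2 suggest that it shows the second quantity. The sensitivity lower limits at low prevalence are higher than common small-sample intervals give. The PPV estimate at 20% prevalence also changes with study size: the n = 1000 entry begins "0.93 (0.89,0.96", and the n = 2500 entry has 0.92. True PPV does not depend on n.

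The table is the Protocol's only statement of precision, set beside a 98% minimum for sensitivity and specificity. The low-prevalence n = 1000 cells also bear on a planned estimate. The police cohort is 1,000 people, described as lower risk. Analysis 1a promises estimates by sub-population, and the stage one text assumes 10% seroprevalence when sizing the capillary sample.

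**Working it through.** **Inputs (Protocol, Table 2 and the text above it).** True sensitivity and specificity 0.98; N = 1000 or 2500; prevalence 5, 10, 15, 20 or 25%; perfect reference assay. Expected positives n+ = N × prevalence: 50, 100, 150, 200, 250 for N = 1000, and 125, 250, 375, 500, 625 for N = 2500.

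**Reproducing the printed sensitivity limits.** Draw n+ ~ Bin(N, prevalence) and a ~ Bin(n+, 0.98), and take the 2.5th and 97.5th percentiles of a/n+ over 10^6 studies. This gives 0.932–1.000 at N = 1000, 5% (printed 0.93–1.00) and 0.967–0.992 at N = 2500, 20% (printed 0.97–0.99). Agreement of the 20 printed limits at two decimals, by method:

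| Method | Matches of 20 |
|---|---|
| Simulated percentiles, n+ random | 20 |
| Wald with continuity correction, cut at 1 | 19 |
| Simulated percentiles, n+ fixed | 18 |
| Beta(0,0) posterior | 17 |
| Wald | 16 |
| Arcsine | 15 |
| Jeffreys | 11 |
| Exact (Clopper-Pearson) | 9 |
| Wilson | 6 |
| Uniform-prior posterior | 6 |

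**Cross-check on the PPV estimates.** Analytic PPV = 0.98p / (0.98p + 0.02(1 − p)).
- At 10%: 0.098/0.116 = 0.8448, which rounds to 0.84. Both columns print 0.85.
- At 20%: 0.196/0.212 = 0.9245, which rounds to 0.92. The n = 1000 column prints 0.93.

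The medians of simulated PPV at 20% are 0.9251 (n = 1000) and 0.9248 (n = 2500), which round to the printed 0.93 and 0.92. At 10% they are about 0.846 and 0.845 (0.8452 unrounded), both rounding to 0.85. All ten printed estimates match the medians. Simulated percentiles match 19 of 20 PPV limits; the miss is 0.825 against 0.82.

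**Intervals at the expected result, N = 1000, 5% (49/50).**
- Exact lower limit: 2.5% quantile of Beta(49, 2) = 0.8935.
- Wilson: (0.98 + 3.8416/100 − 1.96 × √(0.0196/50 + 3.8416/10000)) / (1 + 3.8416/50) = 0.9638/1.0768 = 0.895.
- Uniform prior: Beta(50, 2) = 0.8955. Jeffreys: Beta(49.5, 1.5) = 0.9103.
- Printed: 0.93. The gaps are 3.65, 3.5, 3.45 and 2.0 points.

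**All sensitivity lower limits.**

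| N | Prevalence | Table 2 | Exact | Jeffreys | Exact gap, points |
|---|---|---|---|---|---|
| 1000 | 5% | 0.93 | 0.8935 | 0.9103 | 3.65 |
| 1000 | 10% | 0.95 | 0.9296 | 0.9374 | 2.04 |
| 1000 | 15% | 0.95 | 0.943 | 0.948 | 0.73 |
| 1000 | 20% | 0.96 | 0.9496 | 0.9532 | 1.04 |
| 1000 | 25% | 0.96 | 0.954 | 0.957 | 0.61 |
| 2500 | 5% | 0.95 | 0.9373 | 0.9434 | 1.27 |
| 2500 | 10% | 0.96 | 0.954 | 0.957 | 0.61 |
| 2500 | 15% | 0.96 | 0.960 | 0.962 | −0.02 |
| 2500 | 20% | 0.97 | 0.9635 | 0.9648 | 0.65 |
| 2500 | 25% | 0.97 | 0.966 | 0.967 | 0.43 |

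The printed figures have two decimals, so up to half a point of any gap may be rounding.

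**PPV behind the sizing statement (N = 2500, 20%).** True positives 0.98 × 500 = 490; false positives 0.02 × 2000 = 40; 490/530 = 0.9245. Lower limits: exact 0.8986; Wilson 0.8989; Bayes-rule credible interval with prevalence fixed at 20%, 0.9001 (uniform) to 0.9012 (Jeffreys); simulated percentile 0.901; Wald 0.902.

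**The case against.** The Protocol does not say how Table 2 was made, so the simulation account is an inference. Genuine intervals come close on sensitivity. With upper limits cut at 1, continuity-corrected Wald is within 0.0055 of all 20 limits and a Beta(0,0) credible interval is within 0.007. In the 5%, n = 1000 cell they give lower limits of 0.931 and 0.9275, both rounding to the printed 0.93. Analysis 1a plans credible intervals with no stated prior, so 0.93 is attainable under some version of the plan. The table is called illustrative, and no decision rule uses its sensitivity limits.

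Most of this stands as a limit on the point. It does not remove it. Continuity-corrected Wald matches only 15 of 20 PPV limits, and no interval formula applied at the expected counts explains PPV estimates of 0.85 and 0.93. Plain Wald shows no overstatement at 49/50, but its upper limit there is 1.019. The illustrative caveat rests on the imperfect reference assay and does not tell the reader that the columns may not be confidence intervals.

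A reader might infer that precision is overstated by 4 points throughout. The figures do not support that. Four points is one cell after rounding (0.93 against 0.89); it is 3.65 unrounded and 2.0 with Jeffreys. A reader might also infer that the PPV columns are badly wrong or that 2,500 is too few. Neither follows: plain Wald matches 18 of 20 PPV limits, and the 90% PPV statement holds under some methods and narrowly fails under others.

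**Conclusion.** The point holds in a limited form. The limits in Table 2 are very probably sampling ranges of the estimate, labelled as expected confidence intervals. Against exact, Wilson, uniform-prior or Jeffreys intervals, the sensitivity lower limits are optimistic where positives are few. By the exact and Jeffreys limits the excess is 2.0 to 3.65 points at n = 1000 and 5%, 1.3 to 2.0 at n = 1000 and 10%, and 0.7 to 1.3 at n = 2500 and 5%. Elsewhere at n = 2500 it is under 1 point. The claim that 2,500 participants put the PPV interval wholly above 90% at 20% prevalence is borderline and depends on the method, with lower limits from 0.8986 to 0.902.

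This rests on the Protocol's own assumptions (98% accuracy, a perfect reference assay, the listed prevalences), on evaluating intervals at the expected counts, and on the inferred origin of the table. The differences from the standard intervals do not depend on that origin.

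**What to change.** Either recompute Table 2 as the expected limits of the interval Analysis 1a will report, with the method and prior stated and limits to three decimals, or keep the figures and relabel them as the range within which the estimate is expected to fall. Recomputing is better, because readers want the precision of the reported result.

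In either case:
- print the PPV estimates at their true values, the same for both study sizes (0.845 at 10% prevalence, 0.925 at 20%);
- say that the PPV lower limit at 20% prevalence and 2,500 participants is borderline at 90%, and for which interval method the statement holds.

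The cost is one recalculated table and one reworded sentence. Stated precision becomes slightly worse in the low-prevalence cells. The sample size need not change.
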